### **13.Risk analysis of total failure in the data collection process.**

#### a) Validity and Reliability

Validity and reliability are two essential factors to consider when developing and testing any instrument (e.g., the effect of a 6-weeks content knowledge workshop on written test performance) for use in a study. Attention to these considerations helps ensure the quality of our measurement and the data collected for our research.

To start with, the reducing the risk of failure during data collection must analyze What is Reliability? The concept of reliability can be looked at from two sides:

i) Focus on the ability of an instrument to produce consistent measurements. The experiment mainly focuses on the written test, which must refer to the Education Examination Center and form a standard teachingized written test based on experts' evaluation in content knowledge.

ii) Focus on the degree of consistency in the measurements made by an instrument. Reliability only deals with the surface of the measure, regardless of precisely what it is measuring. Thus, a measure can be reliable without being valid.

iii) Concerns with consistency, replicability, dependability: Consistency – test the consistently yields the same score for an individual. Consistency mainly focuses on the surface of the workshop group and standard teaching group. Hence, consistency and reliability mainly deal with validity and reliability.

On the other hand, based on the 6-week content knowledge experiment, we must provide research to answer specific questions. We need to make a plan, outline it, or determine the strategy adopted to collect data. To achieve this goal, we must first clarify the independent variable workshop and the dependent variable students' written test achievements. Besides, other factors, such as validity, are necessary. Including internal validity, external validity, and construct validity. The specific analysis is as follows:

First, because it will confuse research results, it is not controlled and must be excluded. Especially extra variable, extra variable (confounding variables), embodied in students and teachers in the experiment. For example: when experimenting, the temperature of the weather, the mood of teachers and students, teachers month students' sleep and diet. We have no absolute control. But these impact factors happen so often that there is no need to control for them.

Moreover, different selection. The other section is the threat factor of internal effects in the research. Therefore, it is necessary to distinguish the invariable and the extra changeable variable and control the non-experimental facets: one is variable, and the other is unchanged. The varying experimental factors may be a favorite or unfavorable to the experiment. People have biased opinions and different points of view about everything.

Finally, some measures can be taken based on the above collection of the risk of failure during data. But, first, do an excellent job of equal grouping, and control that everything must be the same except the intervention methods of the workshop and standard teaching .

i) We must do an excellent equal group experiment, divided into the workshop and standard teaching groups. Random sampling uses selective measurement and selection methods. First, before the intervention, pre-test measures the original students' content knowledge level. Then, after measurement, they are sorted according to the scores, ranked according to the sequence position, and equally assigned to each group.

ii) People with attitude bias cannot participate in the experiment. If the experimenter finds himself biased, he should avoid wrong opinions.

iii) The experiment must be recorded in detail. The person in charge of the experiment has to make a detailed record of the experiment as a reference for data sources.

iv) We must eliminate the potential confusion of irrelevant variables, make our research reliable, and draw a compelling inference that the relationship between workshop and students' written test achievements.

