## **2.Explain in detail the research design that we have employed in this study**

### **a)The research design outline**

A good research design should have these characteristics: eliminating deviation, avoiding confusion, controlling irrelevant variables, and testing the statistical accuracy of the hypothesis (Wellesma et al., 2010) . In addition, we must follow the basic theoretical knowledge of research and design. Therefore, the following is discussed in detail based on the research outline.

a) To establish a cause and effect relationship between the workshop and students ' written test performance.

The simplest experimental design

- i) Randomly select subjects from College students majoring in physical education.
- ii) Workshop group - receives treatment.
- iii) standard teaching - does not receive treatment.

b) When to use experimental procedures?

- i) Between the workshop and students have written test performance.
- ii) Control for all variables that might influence the outcome.
- c) Used when comparing workshop, and standard teaching group
  - i) Random assignment - assign individuals to random groups.
  - ii) Control over extraneous variables that might influence the relationship - influence in participant selection, procedures, statistics, or the design likely to affect the outcome.
  - iii) Manipulation of the treatment conditions - manipulate the workshop to determine the effect on the outcome.
  - iv) Outcome measures - assess whether the treatment conditions influence an outcome (Students' written test performance
  - vi) Group comparisons - compare students' written-test performance for different treatment.
- f) Guard against threats to validity - guard against false conclusions.

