## **b) Design details**

### **Part Two**

[figure not shown]
This research design refers to the plan or strategy of conducting a six-week content knowledge intervention on students' written test achievements. The experiment design refers to the plan of six specific contents and knowledge that we planned to improve students' written test achievements. The experiment design can be constructed by determining, setting, and establishing variables of students' written test achievements in the experiment. Include independent variable content knowledge, including experimental variables and other variables that exist reliably.

- 1) The first part studies the design process. Next, the research design uses a quantitative research design.

The research design uses a quantitative research design. According to the specific design of the experiment, we intervene with the experimental and choose true experimentally. according to this type of experiment, we adopt type 1 true experimental. It includes the pre-test post-test control group. It combines the samples and periods of the 6-week test on the influence of content knowledge on students' written test achievement and is based on the pre-test post-test control group standard teaching. We focus on students' content knowledge test before the test (before the first week) and after the test (after the sixth week). In the six-week content knowledge intervention, the researcher conducts an experimental and control groups experiment. Individuals in the experimental group receive the experimental treatment, whereas those in the control group do not.

Table 1. Effect of 6-weeks content knowledge workshop on written test performance-  
-research designs

Pre- and Posttest Design		Time →		
Random assignment	standard teaching Group	Pretest Before the first week,	No Treatment	Posttest After the sixth week
Random assignment	Workshop Group	Pretest Before the first week,	Experimental Treatment	Posttest After the sixth week

The second part is an introduction to research and design.

i) Definition of this experiment.

On the one hand, according to the nature of educational evaluation measurement, the experiment belongs to achievement tests because achievement tests are used to examine students' mastery of specific learning experiences that have occurred and to measure students' learning effects (Kellogg, 1997).

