Six weeks' content knowledge is the measurement content. In addition, the test content classification description is based on achievement tests. Achievement tests are divided into comprehensive achievement tests and single-subject achievement tests. Based on the 6-week content knowledge classification, the test belongs to the complete achievement test. Finally, the achievement test is compiled and analyzed. The establishment of achievement tests includes standard teachingized achievement tests and teacher's self-made achievement tests.

This research design is a standard teachingized test because this research achievement test was evaluated by six experts in the field of content knowledge. Six experts, including three American experts and three Chinese content knowledge experts, demonstrated. Three American experts are doctoral supervisors at Ohio State University, and they are essential researchers and discoverers of content knowledge.

ii) Choice is an true experiment.

The experimental control in actual experimental design strictly obeys the three basic principles of repetition, randomization, and local control. In addition, actual experiments comprise the most rigorous and robust experimental methods because of equating the groups through random assignment. In actual experiments, we randomly assign students to workshop groups and standard teaching groups. Individuals in the workshop group receive the experimental treatment, whereas those in the standard teaching group do not. After we administer the treatment, we compile average (or mean) scores on a posttest. One variation on this design is to

obtain pretest as well as posttest measures or observations. When we collect pretest scores, we will compare net scores (the differences between the pre-and post-test).

At the same time, in the design of the influence of 6 weeks' content knowledge on students' written test achievements, we must: a) Randomly select and allocate subjects. b) Accurately manipulate independent variables. c) Strictly control the effect of extra variables or evenly disperse interference variables.

Table 5. Two-way Breakdown of 6-weeks Content Knowledge Design

Content		CAQs	MAQs	T/F AQs	SAQs	EAQs	Knowledge	Understanding	Application	Analysis	Synthesis	Judgment	Score
Sports Training Design	Classify				√	√	-	-	5	5	5	-	15
	Application					√							
Basketball Class Hour Teaching Plan	Objectives				√	√	5	5	-	5	5	-	20
	Contents												
	Steps				√	√							

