## **10. Experiment the strengths and weaknesses**

### **a) The strengths**

i) True experiments are the most rigorous and robust experimental designs because of equating the groups through random assignment. We randomly sign participants to different conditions of the experimental variable. Individuals in the experimental group (Workshop group) receive the experimental treatment, whereas those in the control group (standard teaching group) do not.

ii) pretest-posttest control-group ensures the equality of experimental (Workshop group) combination control (standard teaching group) group before intervention.

ii) Achievement tests are widely used in educational experiments, and students' achievement tests are the most frequently tested in educational situations. Six weeks' content knowledge is the most basic test for students' written test achievement in an academic position. Generally speaking, after the end of a semester, the achievement tests are conducted, and the achievement tests are used to test later. The scores of students participating in the achievement tests can be compared with the norm data. In this experiment, after learning content knowledge for six weeks, students test it, and the test method and process are the same as achievement tests.

iii) Achievement tests include two types: An academic achievement test and a comprehensive achievement test. A study on the influence of six weeks' content knowledge on complete achievement tests students' achievement. In this study, the content knowledge is classified into six categories, and the comprehensive tests of the six categories meet the comprehensive achievement test standard teachings of achievement tests. The comprehensive achievement test can be either a single test or a complete set of tests. This study's 6-week content knowledge test can use either one of the extensive achievement tests, which is flexible.

iv) Group tests can save human resources and time. We can complete two tests within six weeks and collect 52 students' content, knowledge, achievements, and learning materials within six weeks. Moreover, group tests have been widely used in education.

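### Random assignment is claimed, but the only allocation procedure written (pretest, sort, rank, split equally) contains no chance step and no rule from rank to arm

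*Protocol*

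**What the plan says.** Section 2 a) (research design outline) opens with a causal aim: "To establish a cause and effect relationship between the workshop and students", that is, their written test performance. It lists as a feature of the design "Random assignment - assign individuals to random groups".

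Section 2 b) labels both rows of Table 1 as randomly assigned. Under its item ii) it states "In actual experiments, we randomly assign students to workshop groups and standard teaching groups" and sets as a requirement "Randomly select and allocate subjects". For the analysis it adds "When we collect pretest scores, we will compare net scores (the differences between the pre-and post-test").

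Section 10 a) makes this the first strength of the study: "True experiments are the most rigorous and robust experimental designs because of equating the groups through random assignment". None of these places says how the assignment is made.

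The steps appear once, in section 13 a) i), as a safeguard for equal groups. The pretest comes first. "Then, after measurement, they are sorted according to the scores, ranked according to the sequence position, and equally assigned to each group".

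**The concern.** An allocation that is meant to be random needs a step in which chance decides the arm. Section 13 a) i) is the only text that staff could follow to form the groups, and it has no such step. It orders the students and divides them equally, but leaves open who or what decides which of two neighbouring students goes to the workshop.

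Balance on the pretest is not a substitute. Ranking makes the groups alike on the score that was ranked. Only chance protects against traits that were not measured, such as motivation, which section 10 b) says is hard to analyse, or the outside influences that section 13 says cannot be fully controlled. If someone who has seen the ranking can choose within neighbouring ranks, those traits can differ between arms in a way that no later analysis can remove. The allocation cannot be redone once teaching has started, and the causal aim depends on it.

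**Working it through.** **1. The passages side by side.**

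| Place in protocol | What it gives on allocation | Chance step described? |
|---|---|---|
| 2 a), 2 b) with Table 1, 10 a) | Assertion that assignment is random | No method given |
| 10 b) | Mentions random distribution and an equal-group method | No method given |
| 11 | Random sampling stratified by class | Concerns test papers, not arms |
| 13 a) i), sentence before the steps | Mentions random sampling but explains it as selection | Garbled; concerns sampling |
| 13 a) i), the steps | Pretest, sort, rank, equal split | None; no rank-to-arm rule |

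The claim is made in several places and the procedure in one, and the procedure does not contain what is claimed. The protocol gives no figure on this point to reproduce.

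**2. How many allocations are possible.** Section 10 a) iv) gives 52 students. Two arms of 26 are assumed. Once the ranking is known, a fixed rank-to-arm rule allows 1 allocation. A random draw within 26 adjacent pairs allows 2^26 = 67,108,864. The wording fits either.

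**3. Pretest gap under a fixed rule (illustration).** Assume normal scores and take the expected score at rank i as z_i = Φ⁻¹((52 − i + 1 − 0.375)/52.25).
- Alternating 1-2-1-2: gap = Σ(z_odd − z_even)/26 = 2.520/26 = 0.097. Divided by the SD of these scores, 0.982, this is 0.099, so about 0.10 SD, always favouring the arm that holds rank 1.
- ABBA pattern: about 0.
- Random draw within pairs: mean 0, with an SD of the gap of about 0.027 SD.

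**4. What reaches one content area.** Section 12 tests six areas separately. Assume ranking on the six-area total (section 10 b) hints at a total but does not state it), a between-area correlation r of 0.2 to 0.4, and a pre-post correlation ρ of 0.5 or 0.7. The correlation of one area with the total is √((1 + 5r)/6), which is 0.577 at r = 0.2 and 0.707 at r = 0.4.
- Area pretest gap under 1-2-1-2: 0.097 × 0.577 = 0.056 SD, to 0.097 × 0.707 = 0.069 SD.
- Shift in the area post-test with no true effect, ρ × gap: 0.5 × 0.056 = +0.03, to 0.7 × 0.069 = +0.05 SD.
- Shift in the net score, (ρ − 1) × gap: −0.3 × 0.056 = −0.02, to −0.5 × 0.069 = −0.03 SD.

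**5. False-positive rate at a nominal 5%.** Simulation under the same assumptions, with the area post-test depending on its own pretest only and 20,000 or more runs per setting:
- Fixed 1-2-1-2 rule: about 3 to 4.5% for the post-test alone and about 4 to 4.5% for the net score.
- Random draw within pairs: about 2 to 4% (post-test alone), about 4% (net score), and about 5% with the area pretest as covariate.

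No setting shows an inflated rate for the unadjusted comparisons under a fixed rule. These rates assume that nobody chooses within pairs. They do not describe the effect of such choice, for which the protocol gives no basis for a figure.

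**The case against.** The strongest reply is that the protocol is silent here, not contradictory. It says in several places that assignment is random, and section 13 only adds ranking to make the groups equal. Matching followed by a random draw within pairs satisfies every sentence. This stands as far as it goes: a reader who infers that students were allocated by rank alone goes further than the text. But the protocol does more than leave a detail out. It writes down a procedure, and that procedure can be followed to the letter without any chance step.

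It can also be said that the numerical harm of a fixed rule is small. That stands too. A reader might infer that sorting by score must produce unequal groups or false positives, and the calculations do not support this. A split into top and bottom halves would give a gap of about 1.60 SD, but it contradicts the stated purpose of equal groups and is not a fair reading.

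A reader might further infer from the layout of Table 1 that assignment precedes the pretest, against section 13. A table converted from PDF cannot carry that inference, and the point does not need it.

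Finally, the net-score comparison already uses the pretest, so covariate adjustment is only a modest improvement on it. This is fair, and the adjustment is secondary.

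**Conclusion.** The point holds in this form: the written procedure does not support the claim of random assignment on which the true-experiment label and the causal aim rest. It does not show that allocation was non-random.

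This conclusion rests on the text alone. The figures are illustrations: a pretest gap of about 0.10 SD on the ranking score under alternation, shifts of at most about 0.05 SD in one area, and no inflated error rate. They depend on assumed normal scores, correlations, ranking on a total, and 26 per arm. The last is uncertain, because the workshop lesson plans describe three groups of eight, which is 24 and would leave 52 − 24 = 28 for standard teaching. None of this changes the conclusion.

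The matter should be settled before allocation, because it cannot be repaired afterwards.

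**What to change.** **Allocation.** In section 13 a) i), state that once the pretest is marked and the student list is fixed, students are paired by adjacent rank (26 pairs if there are 52), and one of each pair is assigned to the workshop from a computer-generated random list. The list should be prepared before anyone sees the ranking and be outside the control of teachers and markers. The person in charge of the experiment, named in section 13 a) iii), could hold it if independent of both; the protocol does not say whether that is so. Align sections 2 a), 2 b) and 10 a) with this procedure.

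**Analysis.** In each content-area analysis of section 12, include that area's pretest score as a covariate. The gain over the net-score comparison is modest, and larger if the post-test alone is compared. If the factors of the two-way ANOVA are group and time, its interaction test is the net-score test.

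**If allocation is already done.** Section 10 b) reports group equality in the past tense, so this is possible. If a random draw was made, describe it. If students were placed by rank without one, call the study matched and non-randomised, and remove the claims of random assignment and of a true experiment.

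**Cost.** One random list, an independent holder for it, wording changes in four sections, and one degree of freedom per analysis. No extra students are needed.

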#### **14. Executive Summary**

The employment survey of Chinese students found that it is very difficult for students majoring in physical education to find jobs. The analysis found that the main factor causing employment difficulties is that Chinese students have low written test achievements. However, content knowledge determines the student's written test achievement. Therefore, to solve student employment difficulties, the student's written test achievement and improving the students' written test achievement through experimental design and quantitative research methods.

This experiment aims to use two different teaching methods to intervene in students' learning and find out which teaching method is more conducive to improving students' written test achievement. The experiment will use a 6-week workshop intervention to enhance students' written test achievement. The investigation is divided into workshop groups and standard teaching groups. The most significant difference between the two groups is that the workshop group has oral links and guarantees. The similarities between the two groups are:

a) The same teacher qualifications. b) The same intervention time. c) The same content. d) The same research objects.

Based on content knowledge learning, content knowledge is divided into six categories for detailed intervention. First, we will do a 6-week intervention for two groups (workshop style and standard teaching style). After that, we will assess their progress based on writing tests that the Examination agency develops. The difference between the two is whether there is a video teaching link, and the same is that there are oral links. The entire experiment was carried out in the classroom with the school's consent. Use written exams to check student scores. Students have special teachers responsible for teaching specific content knowledge during class, standard learning after class does not require special care, and the experiment is not risky. This experiment aims to provide a theoretical basis for improving teaching methods. As a result, it increases the employment rate of students and eases the employment pressure of students.
